## 5 Treatment

### 5.1 Study treatment

#### 5.1.1 Investigational and control drugs

All eligible patients will be randomized to receive either sacubitril/valsartan or enalapril. The following study treatment will be provided:

**Table 5-1 Investigational and comparator treatment during the double-blind epoch**

Treatment Arm	Number of Patients	Minimum dose	Maximum dose	Frequency	Formulation	Administration Route
sacubitril/valsartan*	216	24/26 mg	97/103 mg	BID	tablet	oral
sacubitril/valsartan matching placebo						oral
enalapril	216	2.5 mg	10 mg	BID	tablet	oral
enalapril matching placebo						oral

\*Investigational product labeling for sacubitril/valsartan dose levels is based on the total contribution of both components of sacubitril/valsartan and reads, 50 mg, 100 mg and 200 mg. This is equivalent to the sacubitril/valsartan dose levels 24/26 mg, 49/51 mg and 97/103 mg, respectively.

**Table 5-2 Treatment dose level during the double-blind epoch**

Dose Level	Sacubitril/valsartan*	Enalapril
1	24/26 mg or matching placebo BID	2.5 mg or matching placebo BID
2	49/51 mg or matching placebo BID	5 mg or matching placebo BID
3	97/103 mg or matching placebo BID	10 mg or matching placebo BID

\*Investigational product labeling for sacubitril/valsartan dose levels is based on the total contribution of both components of sacubitril/valsartan and reads, 50 mg, 100 mg and 200 mg. This is equivalent to the sacubitril/valsartan dose levels 24/26 mg, 49/51 mg and 97/103 mg, respectively.

Both sacubitril/valsartan and enalapril and their matching placebos will be packaged and labeled by the sponsor in accordance with the US Code of Federal Regulations governing handling of investigational treatments, and will be dispensed by the study physician.

Sacubitril/valsartan and enalapril will be packaged separately to limit the number of pack types, which will allow more flexibility in the drug supply process to cover all the different treatment possibilities (treatment arm and medication dose level), see [Table 5-2](#) and [Table 5-4](#). Packaging type is described below:

- sacubitril/valsartan and its matching placebo will be provided in HDPE bottles.
- enalapril 2.5 mg and its matching placebo will be provided in HDPE bottles.
- enalapril 5 mg and 10 mg and its matching placebo will be provided in blister packs.

Each participating site will be provided with an investigational drug supply containing Dose Levels 1, 2, and 3 and their matching placebos. Bottles and blister packs will be numbered and assigned via an interactive voice response system (IRT). Treatment for the day of randomization and all visits forward will be assigned via IRT. All patients will begin the study on Dose Level 1. Then:

- Sacubitril/valsartan or enalapril dose levels will be force-titrated to achieve the targeted desired dose of 97/103 mg BID or 10 mg BID (Dose Level 3).
- Patients not tolerating the target dose of sacubitril/valsartan 97/103 mg BID or enalapril 10 mg BID (Dose Level 3) can be titrated down to Dose Level 2 (including active medication and matching placebos), if, in the investigator’s judgement, the adjustment/elimination of concomitant medications is not possible or does not alleviate the side effects of concern. See [Section 5.5.5](#).

This study is designed as a double-blind, double-dummy trial to ensure the blinding during the entire course of the study. To maintain the blinding, patients will be required to take their assigned active treatment tablet along with placebo matching the opposite treatment twice daily.

**Table 5-3 Investigational treatment during the open label epoch**

Treatment	Number of patients	Minimum dose*	Maximum dose	Frequency	Formulation	Route
Open-label sacubitril/valsartan**	~346	49/51 mg	97/103 mg	BID	tablet	oral

\*sacubitril/valsartan 24/26 mg BID (Dose Level 1) will be given to patients who completed the double-blind treatment epoch on Dose Level 1 and is available if down-titration is required.

\*\*Investigational product labeling for sacubitril/valsartan dose levels is based on the total contribution of both components of sacubitril/valsartan and reads, 50 mg, 100 mg and 200 mg. This is equivalent to the sacubitril/valsartan dose levels 24/26 mg, 49/51 mg and 97/103 mg, respectively.

**Table 5-4 Treatment Dose Levels during the open-label epoch**

Dose Level*	Sacubitril/valsartan**
2	49/51 mg BID
3	97/103 mg BID

\*Sacubitril/valsartan 24/26 mg BID (Dose Level 1) will be given to patients who completed the double-blind treatment epoch on Dose Level 1. It is also available if down-titration is required.

\*\*Investigational product labeling for sacubitril/valsartan dose levels is based on the total contribution of both components of sacubitril/valsartan and reads, 50 mg, 100 mg and 200 mg. This

Dose Level*	Sacubitril/valsartan**
is equivalent to the sacubitril/valsartan dose levels 24/26 mg, 49/51 mg and 97/103 mg, respectively.	

Open-label sacubitril/valsartan will be packaged and labeled by the sponsor in accordance with the US Code of Federal Regulation governing handling of investigational treatments, and will be dispensed by the study physician. Open-label treatment will be provided for 12-weeks.

- Patients entering the open label-treatment epoch will be given sacubitril/valsartan 49/51 mg BID (Dose Level 2) unless they completed the double-blind treatment epoch on Dose Level 1. Instead, these patients will enter the open-label epoch on sacubitril/valsartan 24/26 mg BID dose (Dose Level 1).
- Study treatment will be force-titrated every 2 weeks to reach the target dose of sacubitril/valsartan 97/103 mg BID (Dose Level 3).

Schedule and dose adjustments will only be allowed if, in the investigator's judgement, the adjustment/elimination of concomitant medications is not possible or does not alleviate the side effects of concern. See [Section 5.5.5](#).

### 5.1.2 Additional treatment

The protocol requires patients to be on stable treatment with guideline-directed therapy for HFrEF, other than ACEis and ARBs, and on an optimal medical regimen to effectively treat comorbidities such as HTN, DM and coronary artery disease.

## 5.2 Treatment arms

Patients/subjects will be assigned at Visit 2 to one of the following two treatment arms in a 1:1 ratio:

- sacubitril/valsartan; or,
- enalapril

## 5.3 Treatment assignment and randomization

At Visit 2, all eligible patients/subjects will be randomized via Interactive Response Technology (IRT) to one of the treatment arms. The investigator or his/her delegate will contact the IRT after confirming that the patient fulfills all the inclusion/exclusion criteria. The IRT will assign a randomization number to the patient, which will be used to link the patient to a treatment arm and will specify a unique medication number for the first package of study drug to be dispensed to the patient.

The randomization numbers will be generated using the following procedure to ensure that treatment assignment is unbiased and concealed from patients/subjects and investigator staff. A patient randomization list will be produced by the IRT provider using a validated system that automates the random assignment of patient numbers to randomization numbers. These randomization numbers are linked to the different treatment arms, which in turn are linked to medication numbers. A separate medication list will be produced by or under the responsibility of Novartis Drug Supply Management using a validated system that automates the random assignment of medication numbers to packs containing the investigational drug(s).

The randomization scheme for patients/subjects will be reviewed and approved by a member of the Novartis Biostatistics Group.

## **5.4 Treatment blinding**

Patients, investigator staff, persons performing the assessments, data analysts and the Clinical Trial Team (CTT) will remain blind to the identity of the treatment from the time of randomization until database lock, using the following methods: (1) Randomization data are kept strictly confidential until the time of unblinding, and will not be accessible by anyone else involved in the study with the exception of the IRT provider generating the randomization code. (2) The identity of the treatments will be concealed by the use of investigational treatments that are identical in packaging, labeling, and schedule of administration, appearance, taste and odor.

A double-dummy design is used because the identity of the study drug cannot be disguised, as the drug products are visibly different. To maintain the blinding, patients will be required to take their assigned active treatment tablet along with placebo matching the opposite treatment twice daily.

Unblinding will only occur in the case of patient emergencies see [Section 5.6](#) and at the conclusion of the study.

## **5.5 Treating the patient**

Sponsor qualified medical personnel will be readily available to advise on trial related medical questions or problems.

### **5.5.1 Patient numbering**

Each patient is uniquely identified by a Subject Number which is composed by the 4-digit site number (e.g., 0501, 0502 etc.) assigned by Novartis and a 3-digit sequential number assigned by the investigator (e.g., 001, 002, etc.). Hence, a 7-digit study patient identification number, e.g., 0501-001. Once assigned to a patient, the Subject Number will not be reused.

Upon signing the informed consent form, the patient is assigned the next sequential number by the investigator. The investigator or his/her staff will contact the IRT and provide the assigned patient study identification number along with the requested identifying information for the patient to register them into the IRT. The site will enter this number on the electronic case report form (eCRF) in the electronic data capture system (EDC).

### **5.5.2 Dispensing the study drug**

Each study site will be supplied by Novartis with investigational and comparator treatment in packaging of identical appearance.

The investigational and control treatment packaging will have a 2-part label. A unique randomization number is printed on each part of this label, which corresponds to one of the 2 treatment arms and a dose level. Investigator staff will identify the investigational treatment package(s) to dispense to the patient by contacting the IRT and obtaining the medication number(s). Immediately before dispensing the package to the patient, investigator staff will

detach the outer part of the label from the packaging and affix it to the source document (Drug Label Form) for that patient's unique subject number.

### **5.5.3 Handling of study treatment**

#### **5.5.3.1 Handling of investigational and comparator treatment**

Investigational and comparator treatment must be received by a designated person at the study site, handled and stored safely and properly, and kept in a secured location to which only the investigator and designees have access. Upon receipt, all study treatment must be stored according to the instructions specified on the labels. Medication labels will include storage conditions but no information about the patient except for the medication number. Clinical supplies are to be dispensed only in accordance with the protocol. Technical complaints are to be reported to the respective Novartis CPO Quality Assurance.

The investigator must maintain an accurate record of the shipment and dispensing of investigational and comparator treatment in a drug accountability log. Monitoring of drug accountability will be performed by field monitors during site visits or remotely and at the completion of the trial. Patients will be asked to return all unused investigational or comparator treatment and packaging at the end of the study or at the time of discontinuation of treatment.

At the conclusion of the study, and as appropriate during the course of the study, the investigator will return all unused investigational and comparator treatment, packaging, drug labels, and a copy of the completed drug accountability log according to the instructions provided by Novartis or its agents.

Medication labels will be in the local language and comply with the legal requirements of the country. They will include storage conditions for the study treatment but no information about the patient except for the medication number.

[figure not shown]
The investigator must maintain an accurate record of the shipment and dispensing of study treatment in a drug accountability log. Monitoring of drug accountability will be performed by monitors during site visits or remotely and at the completion of the trial. Patients/subjects will be asked to return all unused study treatment and packaging at the end of the study or at the time of discontinuation of study treatment.

At the conclusion of the study, and as appropriate during the course of the study, the investigator will return all unused study treatment, packaging, drug labels, and a copy of the completed drug accountability log to the Novartis monitor or to the Novartis address provided in the investigator folder at each site.

#### **5.5.3.2 Handling of other study treatment**

Each study site will be supplied, by Novartis, with open-label sacubitril/valsartan for the 12-week open-label treatment epoch. The IRT will need to be called to receive drug shipments prior to dispensing.

The open-label sacubitril/valsartan packaging will have a 2-part label. Investigator staff will identify the treatment package(s) to dispense to the patient by contacting the IRT and obtaining the medication number(s). Immediately before dispensing the package to the patient,

investigator staff will detach the outer part of the label from the packaging and affix it to the source document (Drug Label Form) for that patient's unique subject number.

Open-label sacubitril/valsartan treatment must be received by a designated person at the study site, handled and stored safely and properly, and kept in a secured location to which only the investigator and designees have access. Upon receipt, all open-label sacubitril/valsartan treatment should be stored according to the instructions specified on the labels. Clinical supplies are to be dispensed only in accordance with the protocol. Medication labels will include storage conditions but no information about the patient except for the medication number. The investigator must maintain an accurate record of the shipment and dispensing of open-label sacubitril/valsartan treatment in a drug accountability log. Monitoring of drug accountability will be performed by field monitors during site visits or remotely and at the completion of the study. Patients will be asked to return all unused open-label treatment and packaging at the end of the study or at the time of discontinuation of treatment.

At the conclusion of the study, and as appropriate during the course of the study, the investigator will return all unused open-label treatment, packaging, drug labels, and a copy of the completed drug accountability log according to the instructions provided by Novartis or its agents.

### **5.5.3.3 Handling of non-study treatment**

The following non-study treatment has to be monitored specifically and recorded in the CRF:

- ACEi/ARB treatment prior to randomization and/or after early discontinuation of study treatment.
- All protocol required background therapy.
- Rescue treatment.

### **5.5.4 Instructions for prescribing and taking study treatment**

Novartis will supply the investigators with all medications sufficient for the course of the study. Patients will be provided with medication packs containing study drug corresponding to their assigned treatment arm and dose level, sufficient to last until the next scheduled visit. Patients will be instructed to hold their morning study medication dose on the day of study visits. Study drug will be administered at the site after pre-dose vital signs, blood samples and assessments are performed. Vital signs will include blood pressure, pulse and respiration measurements. BP will be measured using a standard sphygmomanometer with an appropriate sized cuff and the non-dominant arm in the seated position after 5 minutes of rest, with back supported and both feet placed flat on the floor. Every effort should be made to use the same arm for the patient for all vital signs assessments and where possible, the same person doing the assessment.

In order to adequately blind the study, patients will be required to take their assigned active treatment tablet along with placebo matching the opposite treatment twice daily. Patients will be instructed to take a total of two tablets by mouth twice a day for the duration of the double-blind treatment epoch, as follows:

- one tablet from the sacubitril/valsartan/sacubitril/valsartan matching placebo pack, and;
- one tablet from the enalapril/enalapril matching placebo pack

Table 5-5 summarizes the study drug that will be taken during the double-blind treatment epoch by visit and Table 5-6 summarizes the study drug that will be taken during the open-label treatment epoch.

Forced-titration will proceed according to the following table:

**Table 5-5 Study drug dispense during double-blind treatment epoch**

Visit	Dose Level	Sacubitril/valsartan**	Enalapril	Route	Timing
Rando/Visit 2	1 a,b	24/26 mg or matching placebo BID	2.5 mg or matching placebo BID	Oral	AM & PM
Week 2/Visit 4	2 ce	49/51 mg or matching placebo BID	5 mg or matching placebo BID	Oral	AM & PM
Week 4/Visit 5	3 d	97/103 mg or matching placebo BID	10 mg or matching placebo BID	Oral	AM & PM

\*\*Investigational product labeling for sacubitril/valsartan dose levels is based on the total contribution of both components of sacubitril/valsartan and reads, 50 mg, 100 mg and 200 mg. This is equivalent to the sacubitril/valsartan dose levels 24/26 mg, 49/51 mg and 97/103 mg, respectively.

a. Initial starting dose (Level 1) Eligible patients will be randomized via IRT to either sacubitril/valsartan or enalapril, Dose Level 1.

b. Available after Rando/Visit 2 to end of double-blind treatment epoch only if Dose Levels 2 and 3 are not tolerated despite modification of other non-disease-modifying HF medications and re-challenge.

c. Only if Dose Level 3 is not tolerated despite modification of other non-disease-modifying HF medications and re-challenge.

d. This target Dose Level must be maintained for as long a duration as possible. If down-titration is necessary due to side effects, the patient should be re-challenged as soon as medically possible per the investigator's judgment.

e. The evening dose of study medication prior to Week 4/Visit 5 must be taken no less than 12 hours before the hemodynamic assessment time scheduled for Week 4/Visit 5. See Section 6.4.1.

- At Randomization on Day 1 (Visit 2), eligible patients will be randomized via IRT to either sacubitril/valsartan or enalapril. All patients will start at Dose Level 1 (2.5 mg enalapril or 24/26 mg sacubitril/valsartan, BID).
- At Week 1 (Visit 3), patients will return to the study center for a safety assessment only. Study medication will not be up-titrated.
- At Week 2 (Visit 4), patients will be force-titrated to Dose Level 2 (5 mg enalapril or 49/51 mg sacubitril/valsartan).
- At Week 4 (Visit 5), patients will be force-titrated to the target dose, Dose Level 3 (10 mg enalapril or 97/100 mg sacubitril/valsartan and remain on this target dose for 8 weeks through the evening dose prior to Week 12 (Visit 6).
- At Week 12 (Visit 6), patients will have the final dose of double-blind treatment medication administered in the clinic after pre-dose assessments have been completed. Drug accountability will be performed and all double-blind treatment medication will be returned to the site.
- All patients that complete the 12 week (Visit 6) double-blind treatment epoch will proceed into the 12-week open-label epoch on sacubitril/valsartan.
- Open-label sacubitril/valsartan will be dispensed at Week 12 (Visit 6) with patient instructions **NOT** to start their open label-treatment until the evening after completing a 36-hour wash out. All patients will have the wash out in order to maintain the blinding of the core study.

All dose levels will be available throughout the study. Dose adjustments to lower dose levels may be made at any time at both scheduled and unscheduled visits only if indicated for blood pressure control/tolerability reasons.

All study treatment assigned by the IRT will be recorded/databased in the IRT.

All dosages prescribed and dispensed to the patient and all dose changes during the study must be recorded in the IRT and on the Dosage Administration Record eCRF.

Study medication should be taken twice daily with a glass of water with or without food. Prior to scheduled study visit days, instruct the patient to have nothing by mouth after midnight and to take study medication after vital signs and study assessments are taken by the study coordinator at the investigator site.

If the patient misses taking any study drug dose, he/she should take it as soon as possible and within 4 hours of the scheduled dose time. If the patient is unable to take the missed dose within 4 hours of the scheduled dose time, he/she should skip the missed dose and return to his/her regular study drug administration schedule.

The investigator must promote compliance by instructing the patient to take the study treatment exactly as prescribed and by stating that compliance is necessary for the patient's safety and the validity of the study. The patient must also be instructed to contact the investigator if he/she is unable for any reason to take the study treatment as prescribed.

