Study design	This study will use a multicenter, randomized, double-blind, double-dummy, parallel group, active-controlled, forced - titration, 12-week design in patients with heart failure and reduced ejection fraction (HFrEF) $\leq$ 40%. The study duration is a maximum of 30 weeks with 8 scheduled outpatient visits. Patients will enter a screening epoch up to 6 weeks to assess eligibility requirements and to confirm patients are on stable treatment with guideline-directed therapy for HFrEF, other than ACEis and ARBs. Patients will then be randomized to either sacubitril/valsartan

	
or to enalapril starting doses (Dose Level 1), according to the product label(s). Forced titration will occur every 2 weeks to reach the target dose of sacubitril valsartan or enalapril (Dose Level 3). Dose adjustments will only be allowed if indicated per protocol defined safety and tolerability criteria and investigator judgement, or if the investigator believes that adjustment/elimination of concomitant medications is not possible or does not alleviate the side effects of concern. After 12 weeks of double-blind treatment, patients will continue into the 12-week open-label extension epoch.

Population	
The study population will consist of male and female patients, ≥ 50 years of age with a history of hypertension (HTN) and heart failure (NYHA Class I-III) with a reduced ejection fraction (HFrEF) ≤ 40%. The goal is to randomize a total of approximately 432 patients in a 1:1 ratio (216 per arm) to sacubitril/valsartan or enalapril in approximately 80 centers in the United States. It is estimated that approximately 575 patients will be screened because a screen failure rate of approximately 25% is anticipated based on previous experience.

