##### Double-blind, randomized treatment epoch

- On Day 1 (Visit 2), patients will be randomized to either sacubitril/valsartan 24/26 mg BID or enalapril 2.5 mg BID (Dose Level 1), according to the product label(s) and will return for a safety assessment at Week 1 (Visit 3).
- Study treatment will be force-titrated every 2 weeks to reach the target dose of sacubitril/valsartan 97/103 mg BID and enalapril 10 mg BID (Dose Level 3).

Deviation from the titration schedule or dose adjustments will only be allowed if indicated per protocol defined safety and tolerability criteria (See [Section 5.5.5](#), [Table 5-7](#)) and investigator judgement, if the investigator believes that adjustment/elimination of concomitant medications is not possible or does not alleviate the side effects of concern.

At any time during the 12 week randomized, double-blind treatment epoch, investigators have the option to withdraw patients from study treatment if they develop signs and symptoms of worsening heart failure for which the investigator would like to administer appropriate therapy. (See [Section 5.5.5](#) and [Section 5.5.6](#))

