**1. Adjust Concomitant Medications**

- Dose adjustments/elimination of concomitant medications may remedy the situation before reducing the dose of study treatment. If adjustment of the concomitant medications is not possible or does not alleviate the side effects of concern, THEN;

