**2. Adjust Study Treatment Dose Level**

- Down-titrate study treatment to the previous dose level. The patient may continue receiving the lower dose level for a recommended period of 1 to a maximum of 4 weeks.
- A re-challenge to titrate back up to the target dose level should be attempted at 2 weeks, or when patient is deemed stable. THEN:

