## **15 Appendix 3: Guidelines for the management of blood pressure**

### **Guidelines**

- Investigator should monitor blood pressure closely
- If symptomatic hypotension occurs:
- Correct any treatable cause, e.g. hypovolemia
- If hypotension persists, any antihypertensive drug and non-disease-modifying drugs, such as diuretics, CCBs, nitrates, and  $\alpha$ -blockers, should be down-titrated or stopped first before down-titration of the study drug is considered
- If hypotension persists, the study drug should be down titrated or even temporarily withdrawn. The dose re-challenge and medication adjustment guidelines described in [Section 5.5.5](#) should be adhered to as much as possible.

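### Table 5-5 footnotes b and c allow a lower dose level only after re-challenge, while footnote d and Sections 5.5.4 and 5.5.5 allow the step-down first; the summary and SAP 1.1 also say *or if* where Section 3.1 says *if*

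*Protocol*

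**What the plan says.** Section 5.5.4 of the protocol makes Table 5-5 the schedule for forced titration in the double-blind epoch. Three of its footnotes govern lower levels:

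- Footnote b, on Dose Level 1 after Visit 2: available "only if Dose Levels 2 and 3 are not tolerated despite modification of other non-disease-modifying HF medications and re-challenge".
- Footnote c, on Dose Level 2: "Only if Dose Level 3 is not tolerated despite modification of other non-disease-modifying HF medications and re-challenge".
- Footnote d, on Dose Level 3: "If down-titration is necessary due to side effects, the patient should be re-challenged as soon as medically possible per the investigator's judgment".

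The text of Section 5.5.4 below the table keeps all levels available for the whole study. It lets a lower level be given at any scheduled or unscheduled visit, provided that blood pressure control or tolerability is the reason.

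Section 5.5.5 gives an ordered procedure. Step 1: "Dose adjustments/elimination of concomitant medications may remedy the situation before reducing the dose of study treatment". Step 2 then moves the patient down one level for 1 to 4 weeks, and only after that comes the return: "A re-challenge to titrate back up to the target dose level should be attempted at 2 weeks, or when patient is deemed stable". Step 5, which deals with restart after an interruption, accepts staying on Dose Level 1 or 2 if the patient cannot go higher, with the reason recorded.

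The general condition for leaving the titration schedule appears in two forms. In the protocol summary it is the safety and tolerability criteria with investigator judgement, "or if the investigator believes that adjustment/elimination of concomitant medications is not possible or does not alleviate the side effects of concern"; SAP 1.1 has the same wording. In Section 3.1 it is the criteria "and investigator judgement, if the investigator believes that adjustment/elimination of concomitant medications is not possible", or that such adjustment does not help. Section 3.1 repeats this for the open-label epoch.

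**The concern.** These rules decide when a patient who does not tolerate a dose may be moved to a lower one. Footnotes b and c put re-challenge before the lower level; footnote d and step 2 put it after. The passages also differ on which co-medications are to be changed first, and on whether one condition or two must be met.

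Two sites could therefore handle the same patient differently and each point to protocol text. The same step-down could be logged as a deviation at one site and as compliant at another. On the literal wording of footnotes b and c, a patient who does not tolerate a level would have to be exposed to it again before a lower one is open. That is a participant-safety reason for settling the text. The dose held at the end of the double-blind epoch matters further because patients who finish it on Dose Level 1 start the open-label epoch on Dose Level 1, and all others start on Dose Level 2.

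**Working it through.** No figure in the plan bears on this point, so the check is a comparison of the passages.

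**1. Order of step-down and re-challenge**

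| Place in protocol | When a lower level may be given | Where re-challenge falls | Co-medication step |
|---|---|---|---|
| Table 5-5, footnotes b and c | Only once the higher level has failed despite the other two measures | Before | Non-disease-modifying heart failure drugs |
| Table 5-5, footnote d | When side effects make it necessary | After | None stated |
| Section 5.5.4, text | At any visit, for blood pressure control or tolerability | None stated | None stated |
| Section 5.5.5, steps 1 and 2 | After step 1 | After | Concomitant medication in general, including stopping it |

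The first row cannot be satisfied together with the last. Footnote b's limit on availability also conflicts with the Section 5.5.4 statement that all levels are available throughout.

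**2. An example patient.** Suppose that Dose Level 3 is first not tolerated at Week 10 and that changing co-medication does not help.

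- Under Section 5.5.5, step 2, the patient moves to Dose Level 2. Re-challenge at 2 weeks falls at 10 + 2 = Week 12, and the 4-week maximum runs to 10 + 4 = Week 14. The patient may be on Dose Level 2 at the Week 12 assessment.
- Under footnote c as written, Dose Level 2 is not open until a re-challenge has failed. Until then the patient is on Dose Level 3 or interrupted.

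The two texts give different answers for the same patient at the primary time point.

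**3. Co-medication.** Footnotes b and c name one class of drug. Step 1 names no class. The texts therefore differ on what a site must have tried before reducing study drug.

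**4. *If* against *or if*.** Let A be that the criteria and investigator judgement support an adjustment, and B that changing co-medication is not possible or does not help.

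- Protocol summary and SAP 1.1: A or B.
- Section 3.1: A and B.

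The forms disagree whenever exactly one of A and B holds. If A holds and B does not, the summary permits an adjustment and Section 3.1 does not; the same is true if B holds and A does not.

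**5. Size.** An estimate of the effect on Week 12 dose would need the share of patients with a tolerability problem near Week 12 and the share handled under each reading. An effect on Zc would also need a relation between dose level and Zc. The documents give none of these.

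**The case against.** The strongest defence is that Section 5.5.5 governs. It is the section on dose adjustment, and Sections 3.1 and 5.1.1 and the text under Table 5-6 refer to it. Appendix 3, which puts "any antihypertensive drug and non-disease-modifying drugs, such as diuretics, CCBs, nitrates" ahead of study drug, covers hypotension only and ends by sending the reader to Section 5.5.5. That stands: neither Section 5.1.1 nor Appendix 3 should be counted as a rival rule. But footnotes b and c, the Section 5.5.4 text below Table 5-5, the protocol summary and SAP 1.1 state their own conditions without that reference, and nothing says which text prevails.

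A second defence is that footnotes b and c concern remaining on a lower level after a failed re-challenge. Re-challenge implies that the patient has come off the dose, footnote d uses that order, and step 5 contains a similar idea. This may well be what was meant. Footnote b, however, speaks of availability and does not say so.

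Third, the conjunction has limited practical force. Table 5-7 is labelled guidance and includes an item left to investigator judgement, and the SAP does not instruct sites. So a reader should not infer that Section 3.1 makes Table 5-7 a hard gate. The two wordings still differ.

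Other stronger readings are not supported:

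- A reader might use the PARADIGM-HF hypotension rates in Section 3.6.1 (17.61% and 11.97%) to count affected patients. Those are adverse events rather than down-titrations, the same section says that the present population differs, and no follow-up length is given.
- A reader might infer a clash with inclusion criterion 5 on stable background therapy. That criterion applies before randomization; Section 5.5.7 allows later changes at the investigator's discretion.
- A reader might infer a bias between arms. The wording is the same for both, and treatment is blinded.

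Finally, dose is well documented: SAP 2.3.1 reports who reached Dose Level 3 and why others did not, and SAP 2.4.1 reports dose level by visit. That will show the spread of doses, but not which reading a site followed. The per-protocol exclusions in SAP 5.6 contain no item on dose level or titration.

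**Conclusion.** The concern holds as an inconsistency in the operative titration text. Footnotes b and c cannot be followed together with Section 5.5.5, step 2, for a patient who does not tolerate a dose. They also disagree with footnote d and the Section 5.5.4 text, and they name a narrower co-medication class than step 1. The *if* and *or if* wordings are a separate and smaller conflict.

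The reach is limited to patients with a tolerability problem. The conclusion rests on the wording as written and on the absence of a stated precedence. It does not show that dose at Week 12 or Zc will in fact differ between sites, and no loss of power or precision can be put on it. It is worth correcting because the text is wrong as written and the correction is cheap. No view is taken here on which clinical rule is right.

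**What to change.** Reconcile Table 5-5 footnotes b and c, the Section 5.5.4 text on availability and step-down, Sections 3.1 and 5.5.5, the protocol summary and SAP 1.1 into one sequence. State it once, in Section 5.5.5, and have the other places refer to it. The sequence should settle:

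- whether re-challenge comes before or after a step-down, and whether footnotes b and c concern first moving to a lower level or remaining on it;
- which co-medications are to be changed first;
- whether the criteria with investigator judgement and the co-medication condition are both required, or either one is enough.

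The sponsor makes the clinical choice in each case. The cost is protocol and SAP wording and a notice to sites; no procedure, visit or analysis is added.
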